Arteriovenous fistulas (AVF) are universally acknowledged to be the safest way to access the bloodstream for hemodialysis⁵⁻¹⁰.

Successful AVF require the preservation of native veins, which must dilate after surgery. Guidelines suggest that all suitable forearm and upper-arm veins should be

preserved in patients with chronic kidney disease (CKD) and estimated glomerular filtration rates (eGFR) of less than 30 mL/min/1.73 m², avoiding both peripheral and subclavian venipuncture for any reason¹¹.

Despite this, construction of a viable AVF is often complicated or prevented by veins of insufficient diameter or guality.^{6,7,12} An AVF must 'mature' after creation, which means that the vessel must dilate sufficiently to carry a high blood flow, and the walls of the outflow vein must thicken and become strong enough to endure repetitive needle cannulation and vein dilation in order to remain patent and accommodate repetitive needle cannulation.⁹⁻¹⁶ Vein dilation is one of the key requirements for AVF maturation, although blood flow rates, vessel depth, and the length of the accessible segment of vein are also important. Most surgeons require that the target vein for an AV fistula have a diameter of at least 2.5-3.0 mm in either the upper or lower arm. Unfortunately, many arm veins fail to dilate and enlarge sufficiently after AVF creation, which exposes the constricted vein to arterial flow and associated high wall shear stress. When AVF fail to mature, patients are exposed to the risks of CVC for longer periods, and are subjected to additional surgery and invasive percutaneous procedures, resulting in hospital readmissions, delayed care, and increased costs.¹⁷⁻ ²¹ In a carefully performed multicenter study, the 49% of AVF matured, and another 22% required additional procedures; 28% failed outright.²² Many studies have concluded that it is hard to predict which veins will enlarge to the appropriate size for dialysis use even after preoperative vein mapping studies.^{11,22-25} Clinicians try to refer patients for AVF 6 months prior to the need for HD, to allow for these uncertainties, but this is may not be a realistic approach for all patients.

Another popular approach is to encourage patients to develop their veins by exercising their arms before and after AVF surgery, with the expectation that exercise will increase blood flow to the limb and that this will dilate veins. Patients have traditionally been instructed to apply intermittent compression to the upper arm with elastic bands, to perform hand exercises (e.g. squeezing a soft rubber device) and isometric exercises of the entire arm.²⁶⁻²⁷ Studies have shown some benefits of exercise in promoting vein dilation and possible fistula maturation.²⁸⁻²⁹ The data are more extensive for beneficial effects of intermittent compression, handgrip training, external heat application, and topical agents like nitric oxide on vessel dilation.²⁵⁻³³ Effects of pneumatic compression on venous flow have been widely studied, and are standard of care for the management of lymphedema, prevention of perioperative deep venous thrombosis, and therapy for venous stasis ulcerations.³⁴⁻³⁸

There is an urgent need to find more effective methods to promote vein dilation and develop cost effective, non-invasive devices to help mature fistulae clinically, and help AVF mature. The Fist Assist[®] device (US Patent 8231558) is an external medical intermittent pneumatic compression device that can apply intermittent pressure to the arm. Aside from the direct hemodynamic effects of pneumatic compression, there is evidence for effects on wall shear stress and wall

tensile stress for both arteries and veins, which may stimulate the endothelium to produce nitric oxide that enhances venous dilation.³⁹⁻⁴¹ This research will evaluate the effects of using the Fist Assist[®] device to develop veins prior to AVF surgery.

Device:

The Fist Assist[®] [**Figure 1**] is a self-contained, miniaturized, wearable intermittent pneumatic compression device. The small control unit is integrally attached to an inflatable cuff that is held to the upper extremity using a hook and loop attachment. Patients are able to apply and remove the device themselves using only the contralateral hand. It is battery operated and has a single control to turn it on or off. All pressure and timing parameters are preset at the factory. The bladder is inflated to a pressure of 60 mmHg and held for 20 seconds then deflated to 10 mm Hg pressure for 55 seconds before the next inflation.

The Fist Assist[®] device applies 60 mmHg of compression to the limb, which shuts off after 20 seconds; the device cycles every 75 seconds. In comparison, when a blood pressure is measured as part of routine medical care, pressures of 160-180 mmHg are applied for approximately 45-60 seconds, and a lymphedema garment applies unremitting pressure of 40 mm Hg to an arm for 8-12 hours at a time.

In recently published research, The Fist Assist[®] device was applied for six hours a day for 30 days to 43 patients with new radiocephalic and brachiocephalic AVF, starting one week after surgery. Acceptance of the device was excellent, and no patient suffered fistula thrombosis, or reported pain, skin reactions, or bleeding from the AVF cannulation sites.⁴² In this initial pilot study, significant dilation of AVF outflow veins was demonstrated in patients using the Fist Assist[®] device, compared to control patients using a sham device (P < 0.05).⁴²⁻⁴³

This first proposal of presurgery vein dilation outlines important research that will help to determine optimal roles of the Fist Assist[®] device in improving vascular access outcomes in patients receiving HD, by investigating the effects of the device used both before and after AVF surgery. Early use of this device could potentially allow for vein dilation in patients with advanced chronic kidney disease, preparing veins for AVF creation and improving primary AVF outcomes. Post-surgical use of the device may promote further vein dilation and AVF maturation and reduce the need for secondary procedures to assist maturation. Investigation with this device may uncover a safe and noninvasive way to improve outcomes for ESRD patients, and provide important insights into the biology of successful AVF maturation.

Fist Assist Safety Features: The device has many safety features to prevent patient complications. These include:

1. Patient being able to remove it with ease as its velco and can be easily taken off

2. The device having incorporated firmware to monitor the pressure to ensure it never goes over 60 mm Hg with auto-inflate and auto-vent features. This will ensure steady pressure at 60 mm Hg.

3. A battery monitoring system that ensures there is enough battery power to vent the balloon and turn off the device as the battery decreases to a low level. As the battery deceases to low levels, the device will save enough power to ensure total balloon venting and shut down.**OBJECTIVE:** To determine whether use of the Fist Assist[®] device facilitates vein dilation before AVF creation.

Hypotheses:

Use of the Fist Assist[®] before AVF creation will enhance superficial vein dilation, resulting in increased absolute vein diameters at three months when compared to baseline values.

SPECIFIC AIM:

To determine whether the use of the Fist Assist[®] device for 360 hours over 90 days by patients with advanced CKD prior to AVF surgery results in significant increases in cephalic vein diameters prior to AVF surgery.

SUBJECTS:

Population:

Inclusion criteria: Patients followed in the Nephrology Clinic who are expected to initiate HD will be approached for participation in the study. We will consider all patients with eGFR<30 mL/min.1.73m².³⁹ Patients will be assigned to treatment with the Fist Assist[®].

Exclusion criteria: Refusal/inability to give informed consent, inability to comply with trial requirements, arm infections, and skin disorders that require frequent medical attention. In addition, we will exclude patients with obvious scarring from IV drug use or previous phlebitis. Patients will be excluded if they have previous occluded arteriovenous grafts or fistulae, arterial aneurysms, or arm deep vein thrombosis or any previous vascular surgery on their non-dominant arm. Patients will be excluded they have limited cognitive ability. Patients will be excluded if they have any motor or sensory deficits in their upper arms.

Patients will have a preliminary evaluation of their cephalic vein, measured 5 cm proximal to the styloid process of the radius, and also at the antecubital fossa. Patients will be excluded if there are no detectable superficial veins of at least 1.0 mm diameter, and also if a superficial vein of more than 3.0 mm is present in this lower arm location.

LOCATION: The study will be conducted in the Ambulatory Care facilities at the University of Chicago Medical Center (UCMC).

METHODOLOGY:

Medical History: Medical records of enrolled patients will be reviewed to collect: date of birth, height, weight, ethnicity, and medical history related to factors which may affect vascular health, including but not limited to: dialysis history, diabetes, hypertension, systemic lupus erythromatosis, coronary artery disease, peripheral vascular disease, medication history, and any other factors that contribute to vascular health.

Intervention: The Fist Assist[®] device will be assigned to each enrolled subject by randomization code. All subjects will be asked to use their assigned device twice daily, for two 2-hour sessions, once in the morning and once in the evening. Patients will apply the device to the non-dominant arm above the level of the elbow, and to keep a written log to record use, complications and any problems.

Blood Draws: 10 mL of blood will be obtained from patients being enrolled at the time of their next routine standard of care phlebotomy. These samples will be frozen for future assays of endothelial biomarkers of nitric oxide production and venous dilation, such as asymmetric dimethyl arginine (ADMA) and its metabolites.

Doppler: Patients will undergo examination of their cephalic veins in the Nephrology Clinic, using a portable vascular ultrasound device operated by a co-investigator trained by the UCMC Vascular Lab in this technique. The cephalic vein, a superficial vein originating in the wrist, is the most common vein used for AVF creation. In order to standardize these measurements, the diameter of the cephalic vein and vein wall thickness will be measured in both arms at: (a) 5 cm proximal to the styloid process of the radius, and (b) at the antecubital fossa. The diameter and thickness of the vein will be measured using a B-mode image acquired using a standard ultrasound machine with vascular probe going from outer walls per protocol. Patients will be seated with arms supported at the level of the heart on an exam table with in a room with a temperature of at least 20 degrees Celsius. A layer of at least 1 cm of gel will be applied locally to optimize the ultrasound image quality. Vascular Doppler measurements will be obtained on both arms at the time of consent (baseline), and at the conclusion of therapy. Measurements will be recorded.

Follow Up: Those who are subsequently able to undergo successful AVF creation will be followed clinically for up to 12 months.

Protocol: Informed consent will be obtained by the co-investigators using a written consent form approved by the Institutional Review Board. After informed consent is obtained, patients will receive: physical examination of both forearms; and a vascular Doppler to determine cephalic vein diameters of the nondominant arm. A 10 mL blood sample will be drawn at the next routine phlebotomy.

Patients will be asked to apply the Fist Assist[®] to the upper half of the non-dominant arm. Patients will be asked to use the device twice daily for two 2-hour periods, and report any complications or problems, using a log (see log attached at end of References). Patients will have follow up examinations with measurement of cephalic vein diameter at three months after enrollment.

Outcomes: The primary outcome will be the difference in vein diameter before and after Fist Assist[®] use. Secondary outcomes include: whether or not an AVF was created (versus a synthetic graft or use of a central venous catheter), whether the

resultant vascular access matured sufficiently to be used for HD, and the subsequent exposure of patients to central venous catheters during their first year of HD.

DURATION OF STUDY: All subjects will be enrolled and treated for three months. The duration of the study including data analysis and statistical analysis is expected to be 6-9 months.

| Table 1. Timeline for Study | | | |
|-----------------------------|----------|---------|--|
| Measurement | Baseline | Post-Rx | |
| H&P | Х | | |
| Clinical | Х | Х | |
| examinations | | | |
| Blood sample | Х | Х | |
| Doppler | Х | Х | |

DATA MANAGEMENT: Study data will be collected and managed using REDCap electronic data capture tools hosted at The University of Chicago.

STATISTICAL ANALYSES: The primary outcome of interest will be the difference in the diameter of the cephalic vein between baseline (Pre) and 3 months (Post) in patients treated with the Fist Assist[®] device. Based on prior work, mean vein diameters at baseline are anticipated to be approximately 1.8 mm with a standard deviation of 0.5 mm,⁴⁴ and we anticipate that the standard deviation of the change in diameter is likely to be approximately 0.75 mm.

Effect =[(DsPost)-(DsPre)]

We would consider calculated effect sizes of 0.25-1.0 mm to be clinically meaningful changes that would increase the numbers of patients with vein diameters that meet commonly accepted thresholds for surgical suitability (normally 2.5-3.0 mm). Sample size calculations for a variety of effects are presented in table 1 (below), based on paired t-tests with alpha error of 0.05, standard deviation of the effect size of 0.75 mm, for power of 80% and 90%.

| Table 2 . Sample size required tocompare vein size before and aftertreatment | | | | |
|---|-------|-------|--|--|
| Effect size mm) | 80% | 90% | | |
| | power | power | | |
| 0.25 | 73 | 97 | | |
| 0.50 | 21 | 27 | | |
| 0.75 | 11 | 14 | | |
| 1.00 | 8 | 9 | | |
| 1.25 | 6 | 7 | | |
| 1.50 | 5 | 6 | | |

A secondary aim will be to compare the proportions of treated patients who achieve 3month vein diameters of 2.5 mm and 3.0 mm, to proportions achieved among controls. Given a normal distribution around a mean vein diameter of 1.8 mm with a standard deviation of 0.5 mm, the probability of an untreated wrist vein exceeding 2.5 mm (or 3.0 mm) would be 8.1% and 0.8%, respectively. Given that the standard deviation of the diameter of treated veins is at least 0.75, then the observed probabilities of a treated vein exceeding either 2.5 mm or 3.0 mm can be calculated, and is shown in the table below, any of which could be shown to be a significantly different proportion from the baseline state. The sample sizes required to demonstrate a difference in proportions were calculated using a McNemar test of paired proportions, with the very conservative assumption that 10% of veins that are adequate on preliminary measurement may fall below the cut-off value, due to variation in measurements.

| Table 3. Sample sizes required to demonstrated increased proportions of | | | | | | |
|---|---------|-----------------|-------|---------|-----------------|-------|
| surgically adequate veins | | | | | | |
| Effect | % veins | Required sample | | %veins | Required sample | |
| size | >2.5 mm | 80% | 90% | >3.0 mm | 80% | 90% |
| | | power | power | | power | power |
| 0.25 | 27.4 | 42 | 55 | 10.2 | 83 | 110 |
| 0.50 | 39.6 | 24 | 31 | 17.6 | 45 | 59 |
| 0.75 | 47.5 | 19 | 24 | 27.4 | 28 | 36 |
| 1.00 | 68.8 | 11 | 14 | 39.6 | 18 | 23 |
| 1.25 | 77.9 | 9 | 11 | 47.5 | 15 | 18 |
| 1.50 | 85.3 | 8 | 9 | 68.8 | 9 | 11 |

We intend to study 90 patients, and anticipate effects which should be more than adequate for these purposes.

POTENTIAL RISKS AND BENEFITS TO SUBJECTS: The benefit to the subjects will be that this research could identify interventions that are more likely to result in vascular access patency. The primary risk is that patients may find the device irritating or annoying to wear. The patients will be given a 90 day log with check boxes to determine if any complications occur (see attached log at end of references). All patients enrolled will give informed consent about the study and device to ensure their full understanding and participation.

PAYMENT TO THE SUBJECT: The subject will not incur any cost as a result of participating in the study. The subject will not receive payment for participation in the study. No advertisement will be used to recruit subjects.

PROCESS OF CONSENT: The patient will give informed written consent approved by the IRB prior to participation.

CONFIDENTIALITY: All records will be kept confidential. The subjects will be assigned an identification number prior to entering any information into the computer database. Only study personnel will have access to the database. All forms will be stored and locked in the primary investigator's office immediately. Data will not be shared outside of the University of Chicago.

REFERENCES

- 1. 2017 Annual Data Report. Volume 2, Chapter 3: Vascular Access. United States Renal Data System. Available at: https://www/usrds/prg/2017/view/v2_03.aspx

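### No masking of the primary vein-diameter measurement is described; reading saved, coded images in random order would reduce reading bias at low cost

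*Combined protocol and SAP*

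**What the plan says.** - **Outcome.** The Outcomes paragraph states: "The primary outcome will be the difference in vein diameter before and after Fist Assist[®] use". STATISTICAL ANALYSES defines the effect as the post value minus the pre value in treated patients. The stated hypothesis is directional: larger diameters at three months.
- **Who measures.** The Doppler paragraph has a portable ultrasound "operated by a co-investigator trained by the UCMC Vascular Lab in this technique". The Protocol paragraph has co-investigators obtain consent as well.
- **How.** "The diameter and thickness of the vein will be measured using a B-mode image acquired using a standard ultrasound machine". The paragraph fixes the two sites, outer-wall measurement, seated posture with arms at heart level, a minimum room temperature and a gel layer. It ends with "Measurements will be recorded". It does not mention masking to visit or arm, image storage, coding, repeat reading or reader reliability, and it does not say when the image is measured.
- **Who is treated.** The inclusion criteria say "Patients will be assigned to treatment with the Fist Assist". The Intervention and Protocol paragraphs place the device on the non-dominant arm for everyone. The Intervention paragraph also says "The Fist Assist[®] device will be assigned to each enrolled subject by randomization code", and the secondary aim refers to controls, but no sham device or second group is described for this study.
- **Which arms are scanned.** The Doppler paragraph has both arms scanned at baseline and at the end of therapy. The Protocol paragraph names only the non-dominant arm for the Doppler at enrolment.

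**The concern.** The person at the ultrasound is a member of the study team. At the three-month visit that person can know that the device has been used and on which arm. The diameter of a vein expected to average about 1.8 mm depends on where the calipers are placed, so differences of a tenth of a millimetre are within the reader's discretion. A slight tendency to read follow-up veins larger would pass directly into the primary estimate. The primary analysis is a within-patient change with no comparator to absorb such a shift. A larger sample does not help: the standard error shrinks while a systematic shift stays the same, so the shift becomes more likely to reach significance. At stake is whether a modest positive result could be told apart from reader expectation.

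**Working it through.** **Inputs from the plan (STATISTICAL ANALYSES).** Paired t-test, alpha 0.05, SD of change 0.75 mm, 90 patients planned, smallest effect called meaningful 0.25 mm.

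**Step 1: reproduce the plan's figure.** With noncentrality d·√n/SD and n − 1 degrees of freedom, a two-sided paired t-test for d = 0.25 mm needs 73 patients for 80% power and 97 for 90%, exactly as in Table 2. The other rows agree within one patient. A one-sided normal approximation gives 56 and 78, so the table is two-sided although the text does not say so.

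**Step 2: smallest significant mean change at n = 90.** SE = 0.75/√90 = 0.0791 mm. The critical t with 89 df is 1.987. The threshold is 1.987 × 0.0791 = 0.157 mm, which is 0.157/0.25 = 63% of the smallest meaningful effect.

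**Step 3: chance of significance when the true change is zero.** Let b be a systematic reading shift. The noncentrality is b/0.0791. The values of b are assumptions, since the documents give no figure for reader bias.

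| Assumed b (mm) | Noncentrality | Chance of p < 0.05 |
|---|---|---|
| 0 | 0 | 5.0% |
| 0.05 | 0.63 | 9.6% |
| 0.10 | 1.26 | 24.0% |
| 0.15 | 1.90 | 46.7% |
| 0.20 | 2.53 | 70.6% |

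**Step 4: what coded reading could achieve.** Coding masks only the reading step. If a share f of a total bias b arises there and is removed, the bias left is b(1 − f). The documents give no value for f, so a range is shown.

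| Share removed | b = 0.10 mm | b = 0.15 mm |
|---|---|---|
| 0% | 24.0% | 46.7% |
| 25% | 15.5% | 29.1% |
| 50% | 9.6% | 15.5% |
| 75% | 6.1% | 7.6% |
| 90% | 5.2% | 5.4% |

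**Step 5: workload.** 90 patients × 2 arms × 2 sites × 2 visits = 720 images. If only the non-dominant arm is scanned, the number is 360.

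**The case against.** **The bias sizes are assumed, and significance is not the only yardstick.** Both are true. The plan calls 0.25 to 1.0 mm meaningful. With no true effect and SE 0.0791 mm, a normal approximation puts the chance of an observed mean of at least 0.25 mm at about 3% for a 0.10 mm bias (z = 0.15/0.0791 = 1.90) and about 10% for 0.15 mm (z = 0.10/0.0791 = 1.26). A reader who holds the result to 0.25 mm is less exposed, but the plan does not make that the criterion for success.

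**The scan is already standardised.** Fixed landmarks, posture, temperature floor, gel and vascular-laboratory training do limit discretion. They do not hide visit or arm from the reader.

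**Stronger readings that the documents do not support.**
- *That the diameter is measured live by someone stated to be unblinded.* The text says that an image is acquired and measured, and is silent on timing and masking. That the reader can know visit and arm is an inference from the design.
- *That coded reading would remove most of the bias.* Probe pressure, angle, exact site and choice of frame are fixed at acquisition by someone who may know the visit. Nothing in the documents divides the bias between acquisition and reading. If the same person scans and later reads, some images may also be recognised.
- *That the untreated arm is of no help.* A shift at follow-up common to both arms cancels in a between-arm comparison. Only an arm-specific shift survives. The planned primary analysis makes no such comparison, however.
- *That the risk is larger still because the SD of change is 0.5 mm.* That figure is the plan's baseline SD. Its SD of change is 0.75 mm.

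**Conclusion.** The concern holds as a cheap improvement that should be made. The plan describes no masking of its primary measurement, and its design lets the person measuring know the visit and the treated arm. At n = 90 and SD 0.75 mm, a mean shift of 0.157 mm is enough for significance. An assumed reading bias of 0.05, 0.10 or 0.15 mm with no true effect would give a significant result about 10%, 24% or 47% of the time. These rates rest on the plan's SD, a two-sided test, complete data on 90 patients and bias sizes that are illustrations, not estimates. The documents do not show that any bias is present, and the gain from coded reading cannot be quantified from them.

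**What to change.** Because the diameter "will be measured using a B-mode image acquired using a standard ultrasound machine", the reading can be separated from the scan.

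1. Save the B-mode image for each arm, site and visit under a study code, with date, visit and arm removed.
2. After the last post-treatment scan, have existing staff measure all images in random order, baseline and follow-up mixed. Prefer a co-investigator who did not scan that patient; otherwise use the same one.
3. State that these readings feed the primary analysis, and that any reading made at the visit serves only the 1.0 to 3.0 mm eligibility check.
4. Reconcile the Doppler paragraph (both arms) with the Protocol paragraph (non-dominant arm) on which arms are scanned.

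The cost is image export and storage, a coding list (REDCap is already in use) and the re-reading of up to 720 images. Export from the portable device is assumed to be possible. The report should say what remains: acquisition bias, possible recognition of images by a reader who also scanned, regression to the mean, and change over time without a control.

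### The plan sets no device-off interval before the post-treatment scan, so any short-lived dilation from a recent session would count towards the device's effect.

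*Combined protocol and SAP*

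**What the plan says.** The Doppler paragraph (Methodology) places the scans "at the time of consent (baseline), and at the conclusion of therapy". The Protocol paragraph adds a follow-up visit with "measurement of cephalic vein diameter at three months after enrollment". Neither gives a visit window, a time of day or a minimum time since the device was last worn.

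The Intervention paragraph has the device used "twice daily, for two 2-hour sessions, once in the morning and once in the evening", so a clinic visit can fall soon after a morning session.

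Other scan conditions are standardised: two fixed measuring sites, a minimum gel layer, posture ("Patients will be seated with arms supported at the level of the heart") and a "room with a temperature of at least 20 degrees Celsius".

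On mechanism, the background says that compression affects wall stress in arteries and veins, "which may stimulate the endothelium to produce nitric oxide that enhances venous dilation". It does not say how long such dilation lasts or how large it is.

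The primary effect in Statistical Analyses is the post diameter minus the pre diameter, with no control term.

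**The concern.** The two scans differ in one respect that the plan leaves open. At baseline the vein has never been exposed to the device. At the post scan it may have been compressed earlier the same day. Any acute after-effect of a session can therefore appear in only one of the two measurements, and under the plan's own mechanism it would enlarge the vein. That is a bias in one direction, which a larger sample does not reduce.

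The stated objective is vein dilation before fistula creation, and meaningful change is tied to diameter thresholds for surgical suitability. A vein that is larger only for a while after a session does not serve that purpose. Without the session-to-scan interval, a reader of a positive result could not separate the two explanations.

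**Working it through.** **Inputs from the plan (Statistical Analyses).** N = 90; SD of the change 0.75 mm; paired t-test; alpha 0.05; smallest clinically meaningful change 0.25 mm; anticipated baseline mean 1.8 mm. Sidedness is not stated.

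**Reproducing the plan's figures.** Paired t power with n − 1 degrees of freedom and noncentrality (effect / 0.75) × √n, two-sided 0.05, gives 73 and 97 patients for 0.25 mm at 80% and 90% power. Table 2 states 73 and 97. The other rows agree to within one patient. A one-sided test would give 58 and 79, so the table is two-sided and that is used below. At N = 90 the power for a true 0.25 mm change is 87.9%.

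**Smallest significant mean change.** Standard error = 0.75 / √90 = 0.079 mm. With the two-sided critical value t(89) = 1.987, the threshold is 1.987 × 0.0791 = 0.157 mm.

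**Effect of a transient shift.** The plan gives no size, so a range is assumed: a mean shift b over all 90 patients at the post scan, with zero lasting change. The shifts of 0.05 to 0.20 mm are 3% to 11% of a 1.8 mm vein.

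- Probability of a significant device-favouring result = P(T > 1.987), where T is noncentral t with 89 df and noncentrality b × √90 / 0.75.
- Probability that the observed mean reaches 0.25 mm ≈ 1 − Φ((0.25 − b) / 0.0791).

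| Assumed mean shift (mm) | Noncentrality | Significant, favouring device | Observed mean ≥ 0.25 mm |
|---|---|---|---|
| 0 | 0 | 2.5% | – |
| 0.05 | 0.63 | 9% | 0.6% |
| 0.10 | 1.26 | 24% | 3% |
| 0.15 | 1.90 | 47% | 10% |
| 0.20 | 2.53 | 71% | 26% |

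**Dilution.** These are mean shifts over everyone. If 0.20 mm applied to only half the patients, the mean would be 0.5 × 0.20 = 0.10 mm and the 71% would fall to about 24%.

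**The case against.** The strongest reply is that the documents do not show the problem exists. They describe a possible mechanism, not its time course, and nothing schedules a scan straight after a session; the text merely permits it. This stands: transience is an assumption, and the calculation says only what would follow from it.

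The size can also be questioned. Every assumed shift is below 0.25 mm, so a team that judged the result by its own threshold for a meaningful change would seldom be misled at the lower end of the range. The figures also need the stated mean shift across all 90 patients. Both points stand and limit the weight of the concern.

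A third reply is that the hypothesis speaks of diameters at three months, not of lasting growth, and that the secondary outcomes of fistula creation and maturation test surgical usefulness. This stands in part. Those outcomes do not correct the primary estimate, and the stated purpose of preparing veins for surgery needs a change that outlasts a session.

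Two stronger readings are tempting. A reader might infer that an after-session effect is confined to the treated arm, so that comparison with the other arm could never remove it. That is plausible, but no section says so. A reader might also infer that the open-ended room temperature ("with a temperature of at least 20 degrees Celsius") lets warmth pass as vein growth, since the background lists "external heat application" among influences on vessel dilation. The documents do not support that as a bias. The floor applies to both scans, so varying warmth mainly adds noise; it shifts the mean only if rooms differ systematically between visits, which nothing suggests.

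**Conclusion.** The gap is real but narrow. The plan fixes several scan conditions and omits the one that differs by design between baseline and follow-up: time since the last compression session. If a session leaves short-lived dilation, Post minus Pre is biased towards the device. Over the assumed range, the chance of a significant favourable result with no lasting effect rises from 2.5% to between 9% and 71%. This rests on N = 90, SD 0.75 mm, a two-sided 0.05 test and an assumed shift that the documents neither give nor rule out.

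It would be wrong to conclude that the device's effect is transient, or that 71% is the trial's false-positive rate. The documents establish neither. This is a cheap improvement to the measurement procedure, not a flaw that invalidates the design.

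**What to change.** In the Doppler paragraph, require the post scan to follow a stated device-off interval, for example by booking it before that day's first session or on the day after the last session. The length is for the investigators to choose and justify, since the documents give no time course. Record the clock time of the scan, compute the interval from the Time Off entry already on the patient log, and report a sensitivity analysis of the primary outcome that excludes scans inside the interval. If scans have already been done, the log entries may still allow the interval to be reconstructed where scan times are known.

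The cost is a sentence or two of protocol text, one extra data field and slightly less flexible visit booking. The sample size does not change.

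As a secondary measure to reduce noise, match room temperature between the two visits. The other arm can be used to check for a systematic difference between visits. The Doppler paragraph already has both arms scanned each time; the Protocol paragraph mentions only the non-dominant arm at entry, so the two should be aligned to make sure those data exist.
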